Depression Expectancies for Change scale (those with the highest item-total correlations in the original paper on the scale). Researchers will measure participants' positive actions and thoughts (aligning with the goals of cognitive-behavioral therapy) using the Frequency of Actions and Thoughts Scale (FATS). Researchers will also include two multiple-choice questions regarding participants' readiness to make changes toward challenging their depression.

Researchers will measure how acceptable participants find the SSIs with the Credibility / Expectancy Questionnaire, a few items asking if one experienced an Aha! moment during the SSI and how strongly the Aha! moment affected them, and a rating (out of 5 stars) of the intervention's overall quality.

References:

Kroenke K. (2012). Enhancing the clinical utility of depression screening. *CMAJ : Canadian Medical Association journal*, 184(3), 281–282. <https://doi.org/10.1503/cmaj.112004>

Interventions

11 *experimental SSIs* were included for testing. The active comparison SSI is the Action Brings Change Project, an evidence-based SSI for depression. The *passive control* condition aims to hold attention without influencing depressive symptoms or mood (a three-minute video, multiple-choice questions, two-minute reading passage, three-minute writing exercise, all about trout). All 11 experimental SSIs, the active comparison SSI, and the passive control condition are available in browser (<https://osf.io/nqdte>) and downloadable versions (<https://osf.io/ujbdf>).

Data Collection

Researchers have not yet started data collection. Participants will be recruited from the online participant recruitment platform CloudResearch Connect and, if needed, CloudResearch and Prolific. All study activities will take place through the online survey and experience management platform Qualtrics, except participants will be invited to participate in each study session and be compensated through their online recruitment platform. Participants can choose to skip any items in the study, except ones that are critical for an intervention to function properly.

Hypotheses

Primary Hypothesis

For each SSI, we hypothesize that participants assigned to the SSI will report a different extent of change in depressive symptoms between baseline and four-week follow-up than participants assigned to the passive control condition.

Secondary Hypotheses

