1. For each experimental SSI, researchers hypothesize that participants assigned to the SSI will report a different extent of change in depressive symptoms from baseline to four-week follow-up than participants in the active comparison condition.
2. For each SSI, researchers hypothesize that participants assigned to the SSI will report a different extent of change in each secondary well-being outcome (agency, hopelessness, depression change expectancies, readiness for change, frequency of positive actions and thoughts) compared to participants in the passive control. researchers will compare change in all outcomes from baseline to four-week follow-up, as well as from baseline to immediate post-intervention for outcomes collected at all three timepoints.
3. For each experimental SSI, researchers hypothesize that participants assigned to the SSI will report a different extent of change in each secondary well-being outcome (from baseline to week four or baseline to post-intervention) than those assigned to the active comparison condition.
4. For each experimental SSI, researchers hypothesize that participants will rate the SSI as differently acceptable than the active comparison SSI according to CEQ scores, star ratings, and rate of Aha! Moments.
5. We hypothesize that participants who expect they can improve their depression more at baseline will show a different change in depressive symptoms from baseline to week four.
6. We hypothesize that, on average, the SSIs will be more effective at improving all well-being outcomes (from baseline to week four or baseline to post-intervention) than the passive control.

We do not make any specific hypotheses about which SSIs will be more effective or acceptable than others.

Statistical Analysis Plan

Inclusion criteria

Participants will need to be at least 18 years old, be able to read and write fluently in English, and have enough access to the internet to complete two sessions over four weeks. They must also score at least 10 on the PHQ-9 screen (suggesting moderate depression) and pass the bot check (<https://osf.io/kba7v>) during the screen (Kroenke et al., 2001).

All participants who are randomized to an experimental condition (and therefore completed all baseline measures) will be included in analyses. If a participant begins a survey multiple times, researchers will only keep data from the first time.

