Please see the measures document (<https://osf.io/76cfy>) and the data cleaning script (<https://osf.io/jpk38>) for details on measures and recoding. Before sharing the study data, researchers will remove any potentially identifiable information, included in written response items. Deviations from this pre-registration will be documented.

References:

Primary analysis

Researchers will use a mixed-effects linear regression model to test if depressive symptoms decrease more from baseline to four-week follow-up in each of the 12 active conditions compared to the passive control condition. Timepoint is a three-level factor (i.e., baseline, post-test, and week 4 follow up). The model will include a participant identifier as a random intercept.

Using the “lme4” and “lmerTest” packages in R, this analysis will take this form:

```
lmer(depressive_symptoms ~ timepoint * condition + (1|participant_id))
```

Using lmerTest’s default, p-values will be calculated using Satterthwaite’s method for denominator degrees of freedom.

Secondary analyses (matching the hypotheses above):

1. To test if each experimental SSI changes PHQ-9 scores differently from the active comparison SSI, researchers will redo the main analysis, except using the active comparison condition as the comparator.

2. To test if each SSI changes secondary well-being outcomes to a different extent than the passive control, researchers will replicate the primary analysis for each secondary outcome. For outcomes measured at three timepoints, researchers will compare baseline to each timepoint.
3. To test if each experimental SSI changes secondary well-being outcomes to a different extent than the active comparison SSI, researchers will redo analysis #2, but instead use the active comparison SSI as the comparison condition.
4. To test if each experimental SSI differs in acceptability from the active comparison SSI, researchers will conduct a linear regression model testing between-group differences in intervention acceptability for each acceptability outcome at each timepoint the outcome was collected. For these analyses, researchers will drop data from the passive control because it does not make sense to compare satisfaction with a mental health intervention to satisfaction with an educational program about trout.

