5. To test if participants who expect that they can change their depression more at baseline will show a different reduction in depressive symptoms from baseline to week four, researchers will run a linear mixed-effects regression model with depressive symptoms as the DV, timepoint, baseline depression expectancies, and the interaction between the two as predictors, and a participant identifier nested in experimental condition as a random intercept.
6. To test if, on average, the SSIs will change each outcome differently than the passive control, researchers will re-run the main analysis with *experimental condition* re-coded into a two-level factor in which any of the 12 active SSIs will be coded as “active.” The random intercept, participant ID will be nested within experimental condition. For outcomes measured at three timepoints, researchers will compare the baseline to each timepoint

Sensitivity analyses:

1. Researchers will re-run the primary analysis with demographic covariates: age, gender, disability, race, education, relationship status, political party, employment status, household income, and perceived socioeconomic standing (Social Ladder).
2. Researchers will re-run the primary analysis with demographic and baseline mental health covariates: age, gender, disability, race, education, relationship status, political party, employment status, household income, perceived socioeconomic standing (Social Ladder), baseline depression change expectancies, baseline

positive actions and thoughts, baseline readiness for change, baseline agency, and baseline hopelessness.

3. Researchers will test for differential attrition across conditions and by the interaction of condition and each covariate. If researchers find evidence for differential attrition, researchers will conduct a sensitivity analysis re-running primary and secondary analyses accounting for differential attrition using inverse probability weighting. See the analysis script (<https://osf.io/5eya3>) for details.

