Robustness Check: Researchers will not correct for multiple hypotheses in primary and secondary analyses because each test of an intervention's effect is viewed as a separate hypothesis. However, it might be that some statistically significant results detected are false positives that occur due to testing so many hypotheses at once. To examine this possibility, researchers will conduct a robustness check that replicates all analyses that compare an outcome across many conditions correcting for multiple hypotheses using the Benjamini-Hochberg procedure (Benjamini & Hochberg, 1995).

Inference Criteria: P-values will be used as the criterion for statistical significance. Two-sided tests will be used for all analyses. Effects of $p \leq .05$ will be reported as significant, $.05 < p \leq .1$ as marginally significant, and $p > .1$ as nonsignificant.

Missing data handling: Because participants can choose to skip items, there may be some missing data within outcome measures. If one's response to a scale is missing 33% of its items or fewer, researchers will impute a value for each missing item using the mean of the other items of the scale that the participant answered.

If an outcome scale is missing more than 33% of its items, researchers will consider the entire scale to be missing. In these cases, researchers will not impute missing outcome data because linear mixed models' estimates for longitudinal clinical trial data are not improved by outcome data imputation (Chakraborty & Gu, 2009). Researchers will impute missing covariate data as described in the cleaning script (<https://osf.io/jpk38>).

Sample Size: Researchers will aim to recruit 500 participants per intervention condition, except that the passive control condition will have 3X as many participants as the other conditions because it will improve the statistical power of analyses comparing conditions to the passive control. Thus, researchers aim for a total baseline sample size of $n = 7,500$. This sample size will enable us to detect change in depressive symptoms from baseline to follow-up between each intervention condition and the passive condition with an effect size smaller than Cohen's $d = 0.17$, with 90% power and alpha = 0.05. This sample size will also allow us to detect differences in change in depressive symptoms from baseline to follow-up between each intervention condition smaller than $d = 0.19$.

References:

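### The primary week-4 contrast is a raw change-score difference: unbiased, but never adjusted for baseline PHQ-9, so precision is usually given away

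*Combined protocol and SAP*

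**What the plan says.** The primary hypothesis is that each SSI shows a "different extent of change in depressive symptoms between baseline and four-week follow-up than participants assigned to the passive control condition". The Primary analysis section sets out to "test if depressive symptoms decrease more from baseline to four-week follow-up in each of the 12 active conditions compared to the passive control condition", using the model "lmer(depressive_symptoms ~ timepoint * condition + (1|participant_id". It adds: "Timepoint is a three-level factor (i.e., baseline, post-test, and week 4 follow up". Baseline is therefore a row of the outcome. It is not a covariate, and no constraint makes the baseline means equal across conditions.

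Under Sensitivity analyses, item 1 adds demographic covariates. Item 2 reads "Researchers will re-run the primary analysis with demographic and baseline mental health covariates"; the mental health covariates it lists are baseline expectancies, positive actions and thoughts, readiness, agency and hopelessness. Baseline PHQ-9 is in neither list.

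Three other statements bear on the point. Under Inclusion criteria: "They must also score at least 10 on the PHQ-9 screen", and "All participants who are randomized to an experimental condition (and therefore completed all baseline measures) will be included in analyses". Under Sample Size, the passive control arm is tripled "because it will improve the statistical power of analyses comparing conditions to the passive control".

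**The concern.** With a free baseline mean in every condition, the planned contrast subtracts the whole of any chance baseline difference, which fixes the slope of week-4 on baseline PHQ-9 at 1. Adjustment estimates that slope from the data. Under randomisation both approaches target the same treatment difference, but the change score has the larger variance unless the true slope, rho x SD4/SD0, is near 1.

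Precision is at stake, and the plan treats precision as a design goal: it pays for a threefold control arm to get it. The same model form drives the 12 primary contrasts and the other change-from-baseline contrasts (secondary analyses 1, 2, 3 and 6). The acceptability analyses (secondary analysis 4) are not affected.

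**Working it through.** **Plan's own figure.** Inputs from Sample Size and Inference Criteria: 500 per SSI, 1,500 passive control, 90% power, two-sided alpha 0.05.

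Detectable d = (1.960 + 1.282) x sqrt(1/500 + 1/1500) = 3.242 x 0.05164 = 0.167. Power at d = 0.17 is 90.9%. The stated figure (below 0.17) reproduces for a difference in change with no dropout.

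**What the coefficient is.** The fixed effects give one free mean per condition and timepoint. With complete data the fitted means are the observed cell means, so the contrast is (SSI week 4 - SSI baseline) - (control week 4 - control baseline). The model was fitted by REML to a simulated complete data set of 500 versus 1,500. The interaction was -0.748385 and the raw difference in mean change was -0.748385, with two or with three timepoints.

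**Whether the sensitivity analyses help.** Time-constant covariates entered as main effects explain differences between participants and leave the within-participant contrast alone. In the same data set, adding a baseline covariate left the estimate and its SE unchanged (SE 0.23945 with two timepoints, 0.20849 with three). Adding baseline PHQ-9 while its row stayed in the outcome also left the estimate unchanged.

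**Size of the loss, complete data.** The documents give no SDs or correlation, so these are assumptions.

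- Var(change) = s0² + s4² - 2 x rho x s0 x s4
- Var(adjusted) = s4² x (1 - rho²)

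Baseline SD 4, week-4 SD 5. This is the more plausible case, because the entry rule narrows the baseline distribution:

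| rho | Var(change) = 41 - 40 rho | Var(adjusted) = 25(1 - rho²) | Ratio | Participant equivalent, 7,500 x (1/ratio - 1) |
|---|---|---|---|---|
| 0.4 | 25 | 21 | 0.840 | 1,429 |
| 0.5 | 21 | 18.75 | 0.893 | 900 |
| 0.6 | 17 | 16 | 0.941 | 469 |
| 0.7 | 13 | 12.75 | 0.981 | 147 |
| 0.8 | 9 | 9 | 1.000 | 0 |

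- Equal SDs: the ratio is (1 + rho)/2, that is 0.70, 0.75, 0.80 and 0.85 at rho 0.4 to 0.7.
- Normal baseline score truncated directly at the entry cut-off (untruncated mean 6-12, SD 5-6, rho 0.4-0.7): 0.831 to 0.960.
- Simulation check (4,000 runs, SD 4 versus 5, rho 0.5): variance ratio 0.891; type I error 5.3% for the change score and 5.2% for the adjusted analysis.

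**With dropout.** Let a fraction p be lost at random by week 4, and let c be the model's intraclass correlation. The planned model keeps baseline-only participants, so per observed participant its variance is s4² + k² s0² - 2k x rho x s0 x s4 + p(1 - p)(1 - c)² s0², with k = 1 - p(1 - c). Example with equal SDs of 1, rho = c = 0.4 and p = 0.2: k = 0.88, and the variance is 1 + 0.7744 - 0.704 + 0.0576 = 1.128. Adjusted completers have 0.84, a ratio of 0.745. Over p = 0.2-0.3 and rho = 0.4-0.7 the ratio is 0.745-0.890 with equal SDs and 0.866-0.976 with SD 4 versus 5.

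**The case against.** The strongest reply is that nothing is wrong: the planned estimator is valid, matches the hypothesis and meets its stated detectable effect. In the more plausible SD 4 versus 5 case the gain is modest. Power at d = 0.17 rises from 90.9% to 93.6%, 92.4% and 91.4% at rho 0.5, 0.6 and 0.7, and not at all at 0.8. All of this stands and limits how strongly the point can be put.

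A second reply is that the fix is not quite free. The regression version leaves out participants with no post-baseline score, which conflicts with the rule that everyone randomised is analysed. The common-baseline version needs time-specific variances that the planned call lacks. This also stands. The cost is small, and the dropout comparison shows that the regression version still gains after losing those participants.

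Third, the ratios compare true variances, whereas the SE reported by a three-timepoint random-intercept model can be too small. In the simulated data set above, 0.20849 against 0.23945 is about 13% too small, an implied type I error near 8.8%. That is a separate calibration problem, and it arises only if PHQ-9 is collected at post-test, which the text does not settle. It leaves the true-variance ratios intact, and a one-row-per-participant analysis avoids it.

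Fourth, the sensitivity analyses could recover something if covariates were interacted with timepoint. The text gives no model form, so the statement above is limited to main effects and complete data.

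Finally, the lack of bias depends on complete or ignorably missing data. In one simulation (truncated baseline, rho 0.6, about 26% dropout related to baseline in opposite directions by arm) the planned model was off by about 0.03 SD and the adjusted analysis by almost nothing. That single case does not change the conclusion.

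**Conclusion.** The concern holds. The planned week-4 contrast is in effect a raw change-score difference, and no analysis described in the plan adjusts for baseline PHQ-9. The consequence is lost precision. It is not bias under randomisation, and it does not make the plan miss its stated detectable effect.

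The size rests on assumed SDs and correlations. Contrast variance is 2-16% higher than it need be, relative to the planned variance, for rho 0.4-0.7 with SD 4 versus 5; 4-17% under direct truncation at the entry score; and 15-30% with equal SDs. It is zero where the slope equals 1. At SD 4 versus 5 the gain is worth about 900 participants on 7,500 at rho 0.5, but only about 150 at rho 0.7. The secondary outcomes share the model form, but their gain was not quantified; it may be small where the baseline-to-post correlation is high. The change is worth making because it is cheap and leaves the estimand as it is.

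**What to change.** **Simplest sound version.** Regress week-4 PHQ-9 on condition plus baseline PHQ-9, one row per participant, with no random intercept. If post-test PHQ-9 exists, fit it separately, or fit both timepoints jointly with condition-by-timepoint and baseline-by-timepoint terms and time-specific variances.

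**Alternative that keeps participants with no post-baseline score.** Leave baseline in the outcome with one common mean across conditions, using an unstructured covariance.

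**Two shortcuts to avoid.**

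- Dropping the condition main effects while keeping only the random intercept. At SD 4 versus 5 with two timepoints, the model SE is sqrt(20.5/25) = 0.906 of the true SE (20.5 being the average of 16 and 25), which gives a type I error of about 7.6%. At rho 0.7 the actual variance is 1.03 times that of the change score.
- Adding baseline PHQ-9 as a covariate while the baseline row stays in the outcome. The estimate does not move.

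Apply the same change to secondary analyses 1, 2, 3 and 6, using each outcome's own baseline. Leave the acceptability analyses alone.

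**Cost.** One model formula and one or two SAP sentences. No new data are needed, and the protocol states that data collection has not started. The regression version needs a matching line under Inclusion criteria on participants with no post-baseline score. The common-baseline version keeps them but needs a fitting function that allows time-specific variances.

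### Secondary analysis 4 tests the rate of Aha! moments by linear regression without a robust variance or a binary-outcome model, so its standard errors can be too large or too small if rates differ widely between SSIs

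*Combined protocol and SAP*

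**What the plan says.** Secondary Hypotheses, item 4, states that each experimental SSI will differ from the active comparison SSI in acceptability "according to CEQ scores, star ratings, and rate of Aha! Moments". The Measures section describes the Aha! measure as "a few items asking if one experienced an Aha! moment during the SSI and how strongly the Aha! moment affected them". It therefore has an occurrence part and a strength part, and a rate is most naturally built from the occurrence part as yes or no.

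The matching analysis (Statistical Analysis Plan, Secondary analyses, item 4) reads "researchers will conduct a linear regression model testing between-group differences in intervention acceptability for each acceptability outcome". It makes no exception for a binary outcome and mentions neither a link function nor a robust variance. The same item adds "For these analyses, researchers will drop data from the passive control", which leaves 11 experimental SSIs and the active comparison: 12 arms. Under Sample Size, "Researchers will aim to recruit 500 participants per intervention condition". Under Inference Criteria, p-values decide significance and "Two-sided tests will be used for all analyses".

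**The concern.** A yes/no outcome with rate p has variance p(1-p), so arms with different rates generally have different variances. A single linear regression with default standard errors replaces these by one average over all 12 arms. Each comparison with the active SSI then uses a variance set mainly by the ten arms that are not in the comparison. If the compared arms have a smaller variance than that average, the test is too conservative and loses power. If they have a larger one, it rejects too often. More participants do not help, because the ratio of the reported to the true standard error does not depend on sample size.

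The rest of the plan would not catch this. Secondary tests are uncorrected, and the Benjamini-Hochberg robustness check would start from the same p-values. The plan makes no prediction about which SSIs will be more acceptable, so it gives no ground for expecting similar rates.

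**Working it through.** **The plan's own figure.** No power or precision figure is given for Aha! rates. The fully specified figure is for PHQ-9, one SSI against the passive control, "with 90% power and alpha = 0.05". It reproduces: (1.960 + 1.282) × √(1/500 + 1/1500) = 0.167, below the stated 0.17.

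**Inputs.** From the documents: 12 arms, equal allocation among them, 500 per arm planned, two-sided alpha 0.05. Assumed: all Aha! rates, and 450 per arm (90% of 500) where power is computed.

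**Formulas.** For n per arm:
- pooled variance s² = (1/12) × Σ p(1-p) over the 12 arms;
- reported SE of a difference = √(2s²/n);
- true SE for a pair with common rate p = √(2p(1-p)/n);
- SE ratio r = √(s² / [p(1-p)]), in which n cancels;
- actual type I error = 2 × (1 − Φ(1.96 r)).

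**Type I error for a truly equal pair.** A range for the other ten arms means ten evenly spaced rates.

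| Pair | Other ten | s² | p(1-p) | r | Type I error |
|---|---|---|---|---|---|
| 20% | 20-60% | (2.2370 + 0.32)/12 = 0.2131 | 0.16 | 1.154 | 2.4% |
| 50% | 10-40% | (1.7833 + 0.50)/12 = 0.1903 | 0.25 | 0.872 | 8.7% |
| 30% | 30-60% | (2.3833 + 0.42)/12 = 0.2336 | 0.21 | 1.055 | 3.9% |
| 50% | 30-60% | (2.3833 + 0.50)/12 = 0.2403 | 0.25 | 0.980 | 5.5% |
| 30% | 20-40% | 0.2066 | 0.21 | 0.992 | 5.2% |
| 30% | all 70% | 0.2100 | 0.21 | 1.000 | 5.0% |

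Wider assumed spreads give more: 0.6% for a pair at 10% with others at 10-50%, and 10.4% for a pair at 50% with others at 10-30%. The 3.9% and 5.5% depend on even spacing. With the other ten arms bunched inside 30-60%, the figures are 3.5% (pair at 30%, others all 50%) and 6.8% (pair at 50%, others all 30%).

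**Simulation.** The first row gave 2.5% (500 per arm, 40,000 runs) and the second 9.0% (450 per arm, 20,000 runs). Robust standard errors, a two-proportion score test and a logistic Wald test gave 4.7% to 5.5% in every scenario run at 500 per arm.

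**Power at 20% v 27%, 450 per arm, others at 20-60%.**
- Mean variance of the pair: (0.16 + 0.1971)/2 = 0.1786.
- Pooled variance: (2.2370 + 0.16 + 0.1971)/12 = 0.2162.
- SE ratio: √(0.2162/0.1786) = 1.10.
- True SE: √(0.3571/450) = 0.0282. Reported SE: √(2 × 0.2162/450) = 0.0310.
- Power with a correct SE: Φ(0.07/0.0282 − 1.96) = 70%.
- Power with the pooled SE: Φ((0.07 − 1.96 × 0.0310)/0.0282) = 63%.
- Limit for this pair: with the other ten arms at 50%, the largest possible variance, s² = (2.5 + 0.3571)/12 = 0.2381. The SE is then 15.5% too large and power is 58.8%.

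**The case against.** The strongest reply is that linear regression on a yes/no outcome in randomised arms is legitimate: the rate differences are unbiased, and only standard errors and p-values are in question. That stands.

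The pooled variance is also inferred. The plan does not say ordinary least squares, one 12-arm fit or default standard errors. Separate two-arm regressions with equal arms, or robust errors in code, would largely remove the problem. Measure details, recoding and the analysis script sit in external files. The yes/no coding is likewise the natural reading, not a stated one. This lowers confidence, but nothing in the text supplies a robust variance for item 4, and the script is cited only for the attrition analysis.

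A reader might infer that p-values are wrong whenever rates differ. They are not: the error is nil at 30% against 70% and slight for moderate mid-range spreads.

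A reader might also infer that all 11 comparisons are invalid. With the active comparison and one SSI at 50% and the others at 10-40%, only one comparison is a true null, so the 8.7% applies to that test. The other ten involve real differences of 10 to 40 points. The largest change in power among them, at 50% v 40% with 450 per arm, is from 86% to 90%.

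Finally, the point could be stretched to CEQ scores and star ratings. The documents give no spread by arm for either, so no such claim is made.

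**Conclusion.** The point holds in a limited form. Item 4 applies linear regression to a rate and states neither a robust variance nor a binary-outcome model. On the default reading, the tests of Aha! rates can be conservative or liberal when rates differ widely: 2.4% or 8.7% instead of 5% in the two main assumed scenarios, and about 63% power instead of 70% in the power example. For moderate mid-range spreads the error is small.

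These sizes rest on assumed rates, equal arm sizes, yes/no coding and a single pooled fit. The issue touches one component of one secondary acceptability hypothesis. It does not touch PHQ-9, the well-being outcomes or the primary conclusions. Severity is low, but a clearly better specification is available at almost no cost.

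**What to change.** Add one sentence to item 4 of the Secondary analyses. It should say that the Aha! outcome is the yes/no occurrence item, if that is the intention. It should then name one of two analyses:
- logistic regression on condition, reported as a marginal risk difference; or
- the planned linear regression with heteroscedasticity-robust (HC2 or HC3) standard errors.

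The cost is that sentence and one argument in the R code. Sample size and data collection are unaffected, and the linear model's point estimates do not change. If the external script already does this, the sentence only records it. The plan states that data collection has not begun, so the choice can be fixed before any rates are seen.

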A Megastudy of Single-Session Interventions for Depression (Includes analysis plan and
consent form) March 8, 2025

Protocol

Design

Participants will be randomly assigned to one of 13 conditions, with even odds of allocation, except that the passive control condition will have 3X odds of allocation. Researchers will use Qualtrics's "evenly present elements" feature to ensure each condition gets a roughly equal number of participants.

Procedure

1. **Screen.** Participants will be asked to complete the Patient Health Questionnaire (9-item, PHQ-9) to assess eligibility. Next, eligible participants will be asked to consent to participate in the study.
2. **Baseline session.** Participants who consented will immediately begin the first study session, starting with a baseline well-being questionnaire. Next, they will be randomly allocated to one of the 11 experimental SSI conditions, an active comparison SSI condition, or a passive control condition. After they complete the condition to which they were randomized, they will respond to some of the baseline measures again, as well as measures of SSI satisfaction.
3. **Follow-up.** Four weeks later, participants will be invited to a follow-up survey, in which they will complete the baseline well-being survey again.

Participants will be compensated directly after completing each study session. If participants drop out of the baseline session after randomization, they will still be invited to complete the follow-up survey. After each study session, participants will be offered access to a list of online mental health resources (see <https://osf.io/wz5u6>).

Measures

See the "Megastudy Measures" document (<https://osf.io/76cfy>) for information on measures, and the "Timepoints of megastudy measures" document (<https://osf.io/hn83p>) for information on measurement timepoints.

To measure depressive symptoms, researchers will use the reliable and valid Patient Health Questionnaire (9-item). Researchers will consider a change in PHQ-9 score of 5 or greater to be clinically meaningful (Kroenke, 2012). To measure agency, researchers will use the Pathways Subscale of the State Hope Scale, a reliable and valid three-item self-report measure of one's perceived ability to generate plans and work toward goals. To measure hopelessness, researchers will use the reliable 4-item Beck Hopelessness Scale. Researchers will measure depression change expectancies using three items from the

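### Secondary analysis 4 (acceptability) names no baseline covariates, although suitable ones are collected before randomisation; prespecifying them would cost almost nothing and could gain some precision

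*Combined protocol and SAP*

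**What the plan says.** Statistical Analysis Plan, Secondary analyses, item 4: for each acceptability outcome and each timepoint at which it was collected, "researchers will conduct a linear regression model testing between-group differences in intervention acceptability". No covariate is named. For these models "researchers will drop data from the passive control", which leaves the 11 experimental SSIs and the active comparison SSI. Secondary hypothesis 4 defines acceptability "according to CEQ scores, star ratings, and rate of Aha! Moments".

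Protocol, Procedure, item 2 puts the baseline measures ahead of allocation: the session runs "starting with a baseline well-being questionnaire. Next, they will be randomly allocated to one of the 11 experimental SSI conditions". The Inclusion criteria section says that randomised participants have reached that point "and therefore completed all baseline measures", although single items may be skipped.

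Sensitivity analyses, item 2 lists "baseline depression change expectancies" together with baseline readiness for change, agency, hopelessness, and positive actions and thoughts as covariates, but only for a re-run of the primary PHQ-9 analysis. Sensitivity analyses, item 3 does reach the secondary analyses: if differential attrition is found, they are repeated with inverse probability weights. The Benjamini-Hochberg robustness check adds no covariates.

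**The concern.** Analyses 1, 2, 3 and 6 compare change from baseline, so each participant's own pre-randomisation value of the outcome enters the model. Acceptability has no such value, because nobody can rate an SSI before seeing it. Item 4 therefore compares raw means after the session.

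A natural substitute is available. The Measures section says "Researchers will measure how acceptable participants find the SSIs with the Credibility / Expectancy Questionnaire", and the baseline set contains three items on expectancies for change in depression. The constructs overlap, so someone who expects to improve may well rate an SSI as more credible. The sponsor already treats baseline expectancy as possibly prognostic for PHQ-9 change (secondary hypothesis 5).

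Any within-arm variance that these measures explain now stays in the residual and widens the confidence interval of every comparison in item 4. What is at stake is precision, and only in this secondary analysis.

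**Working it through.** **Inputs from the documents.** 500 per SSI arm, 1,500 in the passive control, 7,500 in total, alpha 0.05 and 90% power (Sample Size); two-sided tests (Inference Criteria); 12 SSI arms in item 4. **Assumed input.** r, the multiple correlation within arms between the baseline covariates and the acceptability score. The documents give no value, so a range is shown.

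**1. The plan's own figures.** The detectable standardised difference is d = (1.960 + 1.282) × √(1/n₁ + 1/n₂).
- Total: 12 × 500 + 1,500 = 7,500, which reproduces.
- 500 v 1,500: d = 0.167, consistent with the stated value below 0.17.
- 500 v 500: d = 0.205. The stated value below 0.19 does not reproduce at 90% two-sided power; power at 0.19 is 85.2%. That sentence does not restate its power, and 85% power would give 0.190.

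Both stated effect sizes concern PHQ-9 change. The documents give no power figure for acceptability, so 0.205 serves here only as the unadjusted reference for 500 v 500.

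**2. Effect of adjustment.** The residual SD is multiplied by √(1 − r²), and the standard error and detectable d shrink by the same factor. The equivalent gain in sample size is 1/(1 − r²) − 1.

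| r (assumed) | SE factor | SE smaller by | Equivalent extra sample | Detectable d, 90% power | A test with 80% power would have |
|---|---|---|---|---|---|
| 0 | 1.000 | 0% | 0% | 0.205 | 80% |
| 0.2 | 0.980 | 2% | 4% | 0.201 | 82% |
| 0.3 | 0.954 | 5% | 10% | 0.196 | 84% |
| 0.4 | 0.917 | 8% | 19% | 0.188 | 86% |
| 0.5 | 0.866 | 13% | 33% | 0.178 | 90% |

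**3. Cost if the covariates predict nothing.** With 12 × 500 = 6,000 raters and 12 arm means, the residual degrees of freedom are 5,988. Four to six covariate terms bring them to 5,984-5,982. The SE rises by √(5,988/5,984) − 1 = 0.03% to √(5,988/5,982) − 1 = 0.05%.

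**4. Check by simulation** (12 arms of 500, four covariates, 8,000 runs per setting, true d = 0.19). Unadjusted power was about 85% throughout. Adjusted power was 85.1%, 86.4%, 88.7% and 91.9% when the covariates explained 0%, 5%, 10% and 20% of the variance (r = 0, 0.22, 0.32 and 0.45). The formula gives 85.2%, 86.9%, 88.6% and 91.9%.

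All figures assume 500 raters per arm. Drop-out during the session would raise every detectable d, but leaves the SE factors unchanged.

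**The case against.** The strongest reply is that nothing here is wrong. Linear regression on condition is a valid test of secondary hypothesis 4, and unadjusted main models with covariates kept for sensitivity analyses are the pattern of the whole plan. No power target is set for acceptability, so none is missed. All of this stands.

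The size of the gain is also open. At r of about 0.2 or less it is trivial. The case for a higher r rests on the overlap between expectancy and the CEQ. It does not carry over automatically to a star rating of overall quality or to a binary Aha! rate. Baseline PHQ-9 may predict little, because entry requires a score of at least 10. These limits stand too.

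Three stronger readings are tempting, and the documents do not support them:
- A reader might infer that item 4 is the trial's smallest set of comparisons. Analyses 1 and 3 are also 500 v 500, and their week-four contrasts face four weeks of attrition, while satisfaction is rated straight after the session.
- A reader might infer that unequal loss of raters between arms goes unaddressed. The conditional inverse probability weighting in Sensitivity analyses, item 3 extends to secondary analyses. It is a partial answer, since it is triggered only by evidence of differential attrition and is aimed at bias, not precision.
- A reader might take a 5-13% smaller SE as established. It holds only if r lies between 0.3 and 0.5.

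Finally, the linked analysis script was not available. If it already adjusts item 4, the SAP text should say so.

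**Conclusion.** The point holds as an optional improvement in efficiency. As written, item 4 uses no pre-randomisation information, although relevant measures are collected before allocation and named as covariates elsewhere in the plan. The unadjusted comparison remains valid and unbiased under randomisation.

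For the CEQ, the gain runs from nothing at r = 0 to a 13% smaller SE at r = 0.5, and becomes material from about r = 0.3. For the other two outcomes it may be smaller. The direction rests on arithmetic: the possible loss is at most about 0.05% of the SE, and any real prediction beyond that is a net gain. The size rests wholly on the assumed r.

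**What to change.** In Secondary analyses, item 4, prespecify baseline depression change expectancies (the main covariate), readiness for change, agency and hopelessness as covariates for each acceptability outcome. Baseline PHQ-9 is optional. Handle missing baseline values with the covariate imputation already planned under Missing data handling, and report the unadjusted model alongside. Keep the conditional weighting analysis for differential attrition as it is.

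The cost is one line in the SAP and one in the analysis script. No new data are needed, and the estimate is still a difference in means (for the Aha! rate, in proportions) between SSIs. The Data Collection section says that collection had not started, so the change could be made before any results are seen. If it is made later, it should be recorded as a deviation, as the plan already requires.
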